4.4. Inclusion/Exclusion Criteria

Participant inclusion criteria

We will recruit 66 dyads (n=132) to participate in a randomized control trial of the adapted couple-based intervention. We anticipate we will need to screen 450 individuals to obtain 66 eligible dyads (n=132). Dyads are eligible to participate if

- (1) both partners are ≥ 18 years old,
- (2) both identify each other as their intimate partner, family member, friend, or other person within their social network,

- (3) the relationship has existed at least 3 months,
- (4) both report feeling safe participating with their partner in the study,
- (5) neither reports any severe physical or sexual violence perpetrated by the other partner in the past year,
- (6) both are able to provide informed consent and follow study procedures, and
- (7) both are fluent in Russian.

In addition, the “index case” (partner initially recruited from AIDS Center) must

- (1) be confirmed HIV+ by the AIDS Center,
- (2) have been on ART at least 3 months,
- (3) not be virally suppressed according to the AIDS Center standard (<500 copies/ml), and
- (4) report injecting any drug in the past year.

“Partners” may be HIV- or HIV+ and may or may not be a PWID. Because dyad dynamics may depend on the sex of the “index case”, women will be the “index case” in at least a third of dyads. If both partners meet eligibility criteria, both will provide consent, complete the baseline assessment, and be randomized to study arm.

Participant exclusion criteria

Individuals who do not meet inclusion criteria or who meet any of the following criteria will be excluded from the study.

- (1) unable to provide informed consent,
- (2) unwilling or unable to participate in study procedures,
- (3) any condition that, in the opinion of the principal investigator and research staff, would make participation in the study unsafe, complicate interpretation of study outcome data, or otherwise interfere with achieving the study objectives.

4.5. Study Enrollment. The Baseline Visit will be conducted remotely by phone or computer with participants. At the Baseline Visit, the participants will provide informed consent, be enrolled in the study, complete the baseline assessment through Qualtrics, and self-collect urine and hair samples (if HIV-positive), which will then be mailed to the GHRCCA research staff.

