4.6.3. Immediately Post-Intervention (IPI) Visit (for all participants)

The IPI will be conducted by phone/video call or in-person in GHRCCA’s field office (post-COVID). Prior to the visit, an RA will mail an IPI kit to participants containing materials to self-collect hair and urine samples. For in-person visits, participants will self-collect samples at the GHRCCA field office. The following procedures/assessments will be performed at the IPI visit:

1. The RA will verify the participants by the name on the record and update the **Locator Information Form**;
2. The RA will send the **IPI Assessment** through Qualtrics;
3. The RA will conduct an **EMD** test and will check in with the participant regarding EMD uses and resolve any issues;
4. Participants will self-collect urine samples and hair samples to measure biological levels of medication adherence. These samples will be mailed to GHRCCA staff.
5. At the participant’s next regular AIDS Center visit, the nurse will obtain an additional **blood sample** to conduct dried blood spot sampling and measure levels of medication in the body

4.6.4. 3-month and 6-month Follow-Up Visits (for all participants)

Three- and six-month Follow-Up Visits will be conducted by phone/video call or in-person in GHRCCA’s field office (post-COVID). The following procedures/assessments will be performed at the 3- and 6-month follow-up visits:

1. The RA will verify the participants by the name on the record and update the **Locator Information Form**;
2. The RA will send the **3- or 6-month follow-up assessment** through Qualtrics;
3. At the **3-month** follow-up, the RA will conduct an **EMD** test and will check in with the participant regarding EMD uses and resolve any issues. At the **6-month** follow-up, the participant will mail the **EMD** back to the RA.
4. After the **6-month** follow-up, the RA will administer the Exit Interview;

4.6.5. Pilot study assessments. Participants in both arms will receive the same schedule of assessments. There will be four main repeated assessment occasions: baseline “pre-intervention”, immediately post-intervention (IPI), 3-month and 6-month follow-up. The primary adherence outcome will be proportion of prescribed doses taken as measured by EMD. Study assessments will be delivered remotely through Qualtrics.

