4.6.11. Safety, Acceptability, Feasibility, Retention and Implementation Data. Intervention safety will be assessed through adverse event reporting by study and clinic staff and an exit interview asking about any negative experiences during the intervention. We will assess acceptability and feasibility of the adapted intervention and biological testing. Both partners will be assessed at the end of each intervention session on satisfaction and obstacles to participation. A brief survey will ask about participants' experiences with biological sample collection. We will track the number of participants retained in the study. For those who drop out, we will attempt to contact them to determine the reason. Staff will be asked questions about intervention delivery, specimen collection and challenges and facilitators of implementation.

4.6.12. Sample size and power considerations for the pilot RCT. We can estimate power for this study based on previous studies.^{33,35} Based on Project Renaissance attrition rates,³³ we anticipate there will be no more than 10% attrition throughout the study. Power analyses were conducted with G*Power⁴⁹ (v3.1.0) using a repeated measures within-between ANOVA approach and $\alpha=.05$. With 30 dyads per arm, we would have 80% power to detect a medium effect size ($f=.15$). Thus, we will recruit 66 couples and aim to have 60 for analysis.

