### **3.2.3. Biological Measures.**

*Dried blood spot (DBS) samples* were collected from HIV-positive participants at their regular AIDS Center visit to assess feasibility and acceptability of the biological collection process and measure biological levels of medication. A nurse collected DBS samples by venipuncture, using a pipette to spot blood directly onto Whatman 903 ProteinSaver cards. The cards will be air-dried, individually packaged in a plastic bag with desiccant, and transferred to a -20 to -80°C freezer for storage. Only samples of participants on tenofovir-based regimens were shipped to the US.

*Hair samples.* Participants self-collected hair samples at baseline and immediately post-intervention to measure ART adherence levels. To collect hair samples, participants cut a small thatch of hair (~50 strands of hair) close to the scalp from a bottom layer of their hair. Hair was placed in a piece of tinfoil and inside a Ziploc bag labeled with their study ID. Participants shipped samples to GHRCCA staff, who then batch shipped samples to the US for testing.

*Viral load.* Participants are tested for viral load levels during every patient visit at the AIDS Center, which occurs every six months. Viral load data were abstracted from the AIDS Center electronic medical record at the closest visit prior to the baseline assessment and at the closest visit to the six-month follow-up assessment.

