#### 4.2. Dependent Variables

The dependent variables in this analysis are:

1. EMD measured ART adherence – Number of days EMD is opened from baseline to six-month follow-up (0 to 180 days) among participants in each arm.
2. Biological measures of ART adherence – Number of participants in each arm who are virally suppressed and adherent as measured through biological testing.
3. Self-reported ART adherence – Assessed by a validated three-item ART adherence scale. The three items are: 1) *Days taken* -- number of days the patient missed at least one dose of their medication (number of days, 0-30); 2) *Frequency* -- how often the patient took their medication in the way they were supposed to in the past 30 days (never/rarely/sometimes/usually/almost always/always); and 3) *Rating* – how good a job the patient did in taking their medication in the way they were supposed to in the past 30 days (very poor/poor/fair/good/very good/excellent). Responses were then linearly transformed into a scale of 0 to 100 (higher scores indicate greater adherence). The average score across the three items was calculated to represent overall adherence. Scale reliability among this sample was high (Cronbach's  $\alpha = .90$ ).
4. Uptake of OST – Number of participants who reported they were currently taking OST at the six-month follow-up.

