#### 4.4. Covariates

As appropriate in the analyses, multivariable modeling of changes in ART adherence will include adjustment for the following participant-level characteristics:

- a. Age
- b. Sex
- c. Partner HIV status
- d. Baseline levels of adherence

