#### 4.5. Statistical Analysis Methods

Descriptive statistics of key independent variables and covariates will be summarized within each arm using frequencies or means (standard deviations) as appropriate. Overall participation rates will be reported in each arm based on the proportion of baseline participants who completed the six-month follow-up assessment.

To test **hypothesis 1 (H1)**, we will conduct t-tests to assess for differences in ART adherence rates over six months (0 to 180 days) between study arms.

To test **hypothesis 2 (H2)**, we will conduct chi-square tests to assess for differences in biological measures of ART adherence between study arms. Adjustments for small sample sizes will be made as appropriate.

To test **hypothesis 3 (H3)**, we will conduct generalized linear mixed modeling to assess for change in self-reported ART adherence from baseline to the six-month follow-up period and compare between arms. Generalized linear mixed modeling will be used to account for the effect of response clustering within participants. Models will adjust for the covariates specified above (section 4.4) and include random effects for dyad and intercept.

The model testing H3 is summarized as Equation H3:

$$\begin{aligned} \text{ART adherence} = & \text{Intercept} + B_1(\text{Arm}) + B_2(\text{Categorical variable corresponding to timepoint of adherence assessment; two degrees of freedom}) + \\ & B_3(\text{Arm * Timepoint of adherence assessment; two degrees of freedom}) + B_4(\text{Baseline adherence level}) + B_5(\text{Partner HIV status}) + B_6(\text{Respondent Age}) + B_7(\text{Respondent Sex}) + \text{Error} \\ & + \text{Random effects for the clustering within participant across timepoints and by dyad.} \end{aligned}$$

If the statistical test for the interaction between arm and timepoint is significant at the  $\alpha=0.05$  level, then we conclude that study arm significantly impacts the change in ART adherence. Within arm, adjusted estimates of changes in adherence will be presented along with 95% confidence intervals.

To test **hypothesis 4 (H4)**, we will conduct chi-square tests to assess for differences in uptake of OST between study arms. Adjustments for small sample sizes will be made as appropriate.

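### Hair and dried blood spot drug levels are cut to adherent yes/no with no stated cut-off and compared by chi-square, and the baseline hair level is not used

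*SAP*

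**What the plan says.** SAP 4.2 defines the biological outcome as "Number of participants in each arm who are virally suppressed and adherent as measured through biological testing". For hypothesis 2 (the first secondary hypothesis in SAP 2), SAP 4.5 says "we will conduct chi-square tests to assess for differences in biological measures of ART adherence between study arms", with an unspecified small-sample adjustment where needed. That test has no baseline or other covariate term.

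On sampling, SAP 3.2.3 records that "Participants self-collected hair samples at baseline and immediately post-intervention to measure ART adherence levels". DBS appears only in the post-intervention visit of Protocol 4.6.3, where a nurse takes blood at the next regular AIDS Center visit "to conduct dried blood spot sampling and measure levels of medication in the body". On assay, SAP 3.2.3 says "Only samples of participants on tenofovir-based regimens were shipped to the US".

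The SAP does provide for baseline adjustment in one place. Section 4.4 says "multivariable modeling of changes in ART adherence will include adjustment for the following participant-level characteristics", and its list includes baseline adherence. Only the self-report model (hypothesis 3) is written with that term.

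The only biological threshold in either document is the viral load limit of 500 copies/ml in the eligibility criteria (Protocol 4.4). No concentration cut-off is given for hair or DBS.

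**The concern.** A concentration carries more information than the side of a line on which it falls, and a pilot of this size has little to spare. With no cut-off written down, the split could also be chosen once the data are known, and the result may depend on that choice. The hair baseline is already collected, and it is the natural covariate for hair after the intervention.

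At stake is the precision of the between-arm estimate of drug exposure. Protocol 4.7 makes precise estimation of parameters for the next trial a main purpose of the pilot, and it names continuous as well as dichotomous endpoints.

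**Working it through.** **The plan's own figure.** Protocol 4.6.12 gives 80% power for f = 0.15 with 30 dyads per arm, from a repeated-measures ANOVA at α = 0.05. With four assessments and an assumed correlation of 0.5, λ = 0.15² × 60 × 4 / (1 − 0.5) = 10.8 on 3 and 174 degrees of freedom, which gives 78.6%. That is close to the stated 80%. It is not a power figure for hypothesis 2, and the documents give none.

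**Inputs.** From the documents: 30 analysed dyads per arm and two-sided α = 0.05. Assumed, because the documents give none of them: the cut, the SD, the size of the shift, the baseline correlation ρ, and normally distributed log levels.

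**Step 1: loss from the split alone.** For a small normal shift, the efficiency of a cut at proportion p, relative to the continuous comparison, is φ(z_p)² / [p(1 − p)].

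- 50/50: 0.3989² / 0.25 = 0.64, so 36% lost.
- 70/30: 0.3477² / 0.21 = 0.58, so 42% lost.
- 80/20: 0.2800² / 0.16 = 0.49, so 51% lost.

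This applies to hair and DBS alike. For DBS it is the whole argument, because no baseline sample is listed.

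**Step 2: hair, with baseline also ignored.** Adjusting for baseline multiplies the residual variance by (1 − ρ²), so the Step 1 efficiency is multiplied by the same factor.

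| Cut | ρ = 0 | ρ = 0.5 | ρ = 0.7 |
|---|---|---|---|
| 50/50 | 0.64 | 0.64 × 0.75 = 0.48 | 0.64 × 0.51 = 0.32 |
| 80/20 | 0.49 | 0.49 × 0.75 = 0.37 | 0.49 × 0.51 = 0.25 |

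The loss therefore runs from 36% to 75%.

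**Step 3: what this means in power.** Take 30 per arm, a true shift of 0.73 SD (about what a t-test detects with 80% power at this size) and a cut midway between the arms. The adherent shares are Φ(±0.365) = 0.642 and 0.358.

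- Chi-square: Φ[(0.285 − 1.96 × √(2 × 0.25/30)) / √(2 × 0.642 × 0.358/30)] = Φ(0.26) = 60%.
- Continuous: Φ[0.73/√(2/30) − 1.96] = Φ(0.87) = 81%.
- Baseline-adjusted, ρ = 0.5: Φ[0.73/√(0.75 × 2/30) − 1.96] = Φ(1.31) = 90%.

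The numbers per arm for 80% power are 48, 30 and 23 respectively.

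**Step 4: when the advantage fails.** These results come from simulation with 27 per arm (an assumption: 30 × 0.9) and a 0.5 SD shift. With no assay floor, power is about 28% for chi-square, 20% for Fisher, 44% for the t-test and 50% to 61% for baseline adjustment at ρ = 0.4 to 0.6. Now let values below an assay limit be tied at that limit, with the split made there.

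- Half of values below the limit: t-test about 37%, chi-square 28%.
- About 70% of control values below: the gain over chi-square is only about 1 to 5 points, or nil.
- If the intervention only raises the share with detectable drug (50% to 75%), with detected levels averaging 2 log units (SD 0.8) above the substituted value: chi-square about 47%, t-test 36%.

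**The case against.** The strongest reply is that the size of the loss is idealised. It assumes a normal shift, complete data and no assay floor. Index cases enter the trial unsuppressed (Protocol 4.4), so many low or undetectable levels are plausible, and Step 4 shows that a yes/no test can then match or beat a t-test. This stands. It calls for a below-limit rule, but not for a cut-off left open.

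A second reply is practical. Adjustment needs paired hair samples, and SAP 4.6 rules out imputation. If unpaired participants were dropped, losing 16% of pairs at ρ = 0.4, or 36% at ρ = 0.6, would cancel the gain from baseline (1 − (1 − ρ²) = ρ²). Regimens may contain different drugs, some taken by few people. HIV-positive partners may contribute samples, so dyads matter. DBS timing follows the clinic schedule. All of this stands and shapes the fix. The variety of drugs does not favour chi-square, because a split needs a cut-off for each drug too, and DBS has a single analyte (TFV-DP).

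Stronger readings are tempting, but the documents do not support them:

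- *The plan wastes half the information in a 66-dyad pilot.* Half is a middle value for hair at a 50/50 cut and ρ = 0.5, not a figure that the documents yield. DBS is assayed only in the tenofovir subset, whose size is not stated.
- *The larger trial will get no mean or SD.* SAP 4.1 already commits to means and SDs for interval measures, and Protocol 4.7 to means and proportions with 95% intervals. Concentrations are simply not named.
- *Chi-square is wrong throughout hypothesis 2.* It is conventional for viral suppression.

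**Conclusion.** The point holds as an efficiency and specification weakness. Hair and DBS levels are reduced to an undefined yes/no and tested without the baseline hair value. It is also unclear whether suppressed and adherent form one composite or separate outcomes.

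If log levels shift normally, the split costs about 36% to 51% of the information for hair and DBS over cuts from 50/50 to 80/20. For hair, ignoring baseline as well gives 36% to 75% for ρ from 0 to 0.7. These are ranges under assumptions. With most values below the assay limit, the gain from using levels may be small or absent.

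The severity is modest: this is a secondary outcome in a pilot, and DBS collection is partly a test of feasibility.

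**What to change.** Amend SAP 4.2 and 4.5 as follows.

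- **Hair.** Main analysis: log concentration after the intervention, compared by arm and adjusted for log baseline hair and drug. Enter drug as a covariate or stratum, and pool rare drugs or report them descriptively. Keep participants without baseline hair, through a missing-indicator or a constrained longitudinal model, and reconcile this with SAP 4.6.
- **DBS.** Compare log TFV-DP by arm with linear regression in participants on tenofovir at randomisation, adjusted for time from randomisation to sampling.
- **Analysis set.** Use index cases as the main set, or add a dyad random effect if HIV-positive partners are included.
- **Below-limit values.** State the rule in advance, for example a censored or rank-based analysis once more than a stated share is below the limit.
- **Reporting.** Give between-arm differences with 95% confidence intervals, and name concentrations among the measures summarised by mean and SD.
- **Viral suppression.** Keep chi-square or Fisher, separate from drug levels. Show any adherent/non-adherent split as supportive only, with its cut-off fixed beforehand.

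The cost is SAP wording. No further sample, visit or assay is needed. The downsides are the below-limit rule and a scale less intuitive than a percentage.

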## 2. HYPOTHESES

The **primary** null ( $H_0$ ) and alternative ( $H_A$ ) statistical hypotheses are:

$H_{P0}$ : ART adherence as measured through an EMD throughout the six-month follow-up period will not differ between the intervention and standard of care arms.

$H_{PA}$ : ART adherence as measured through an EMD throughout the six-month follow-up period will be higher in the intervention arm compared to the standard of care arm.

The **first secondary** null ( $H_0$ ) and alternative ( $H_A$ ) statistical hypotheses are:

$H_{S10}$ : ART adherence as measured through biological measures will not differ between the intervention and standard of care arms.

$H_{S1A}$ : ART adherence as measured through biological measures will be higher in the intervention arm compared to the standard of care arm.

The **second secondary** null ( $H_0$ ) and alternative ( $H_A$ ) statistical hypotheses are:

$H_{S20}$ : Changes in self-reported ART adherence from baseline to the six-month follow-up period will not differ between the intervention and standard of care arms.

$H_{S2A}$ : Changes in self-reported ART adherence from baseline to the six-month follow-up period will be greater in the intervention arm compared to the standard of care arm.

The **third secondary** null ( $H_0$ ) and alternative ( $H_A$ ) statistical hypotheses are:

$H_{S30}$ : Uptake of OST at the six-month follow-up will not differ between the intervention and standard of care arms.

$H_{S3A}$ : Uptake of OST at the six-month follow-up will be higher in the intervention arm compared to the standard of care arm.

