## **4. STATISTICAL PRINCIPLES AND ANALYSIS**

### **4.1 Confidence Intervals and P-values**

All statistical computations will be performed by the PI ([name]), who is an epidemiologist, in consultation with quantitative data scientists. For descriptive summaries of study data, the following will be presented:

- Nominal/categorical measures will be summarized using frequencies and percentages;
- Interval or ratio scale measures will be summarized using means and standard deviations;
- Ordinal measures will be summarized depending on the number of levels. An ordinal measure with five levels or less will be summarized as a nominal measure. An ordinal measure with more than five levels will be summarized as an interval or ratio scale measure.

The balance or imbalance of baseline characteristics will be studied and reported, particularly for analyses comparing the two study arms.

Reported p-values will be based on two-sided tests at an  $\alpha=0.05$  unless otherwise specified. When p-value correction is appropriate, Benjamini-Hochberg False Discovery Rate adjustments will be used to address multiplicity and preserve Type I error rate.

Unless required otherwise by a journal, the following rules are standard:

- Test statistics will be reported to two decimal places.
- P-values will be reported to two significant figures. If less than 0.001, p-values will be reported as '<0.001'.
- No preliminary rounding will be performed; rounding will only occur after analysis. To round, consider digit to right of last significant digit: if  $< 5$  round down, if  $\geq 5$  round up.

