#### 4.3. Independent Variables

The key independent variables in this analysis are:

Study Arm – Randomized to the Intervention arm or the SOC arm.

Timing of Assessment – pre-intervention, immediately post-intervention, three-month follow-up, six-month follow-up.

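### The decision rule for self-reported adherence (H3) tests whether the arm difference varies between post-baseline visits, not whether there is a benefit at six months

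*SAP*

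**What the plan says.** SAP section 2 states the second secondary hypothesis as: "Changes in self-reported ART adherence from baseline to the six-month follow-up period will be greater in the intervention arm". Section 1 describes the matching outcome as an arm difference at the six-month follow-up.

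Section 4.3 lists four assessment times: "pre-intervention, immediately post-intervention, three-month follow-up, six-month follow-up".

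Equation H3 in section 4.5 contains:
- arm (B1);
- a time factor, given as "Categorical variable corresponding to timepoint of adherence assessment; two degrees of freedom" (B2);
- the arm-by-time product, also with two degrees of freedom (B3);
- "Baseline adherence level" as a covariate (B4);
- partner HIV status, age and sex, plus random effects for participant and dyad.

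The only decision rule for H3 begins "If the statistical test for the interaction between arm and timepoint is significant at the" 0.05 level and continues "then we conclude that study arm significantly impacts the change in ART adherence". B1 has no part in it. The estimates promised next are adjusted changes within each arm with confidence intervals. No between-arm contrast at month 6 is named.

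**The concern.** Two degrees of freedom mean three time levels. Baseline is already a covariate, so the natural reading is that the outcome rows are the immediate post-intervention (IPI), 3-month and 6-month visits. With IPI as the reference level, the baseline-adjusted arm difference is B1 at IPI and B1 plus the matching element of B3 at month 6. B3 alone measures only how the arm difference moves after IPI. A rule based on B3 alone therefore does not test the hypothesis in section 2.

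The rule fails in both directions. A benefit that appears at IPI and is held to month 6 leaves B3 at zero, so the rule has no basis for declaring an effect. A benefit that appears at IPI and is lost by month 6 makes B3 non-zero, and the rule can then support the conclusion that the arm matters. Protocol section 1.5 gives the short-lived effect of the earlier couples intervention as a reason for strengthening it. The rule can thus miss a durable effect and reward the weakness that the trial is meant to correct.

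The test also has no direction: late harm triggers it as readily as a late benefit of the same size.

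**Working it through.** **Inputs from the documents.** 30 dyads per arm analysed, f = 0.15, alpha 0.05, 80% power (Protocol 4.6.12); two-sided tests (SAP 4.1); four assessments (SAP 4.3); the degrees of freedom and baseline covariate (SAP 4.5).

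**Assumptions.** Neither document gives an SD or between-visit correlation for the three-item scale. I take SD 1, equal correlation rho between all visits (0.3, 0.5, 0.7), one respondent per dyad and complete data.

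**1. The plan's own power figure.** There is none for H3. For the Protocol's repeated-measures within-between ANOVA with N = 60 and m = 4 visits:

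lambda = f² × N × m / (1 − rho) = 0.0225 × 60 × 4 / 0.5 = 10.8, on (3, 174) df, giving 78.6% power.

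This is close to the stated 80%, which is reached exactly at rho = 0.516. So the figure is reproduced if four visits and rho of about 0.5 were used, neither of which is stated. It belongs to a 3-df interaction that includes baseline, not to the 2-df test in Equation H3.

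**2. An effect size on the Protocol's scale.** For arm differences (0, d, d, d) over four visits, the sum of squared deviations is 0.75d², so f² = 0.75d²/16. Setting f = 0.15 gives d = 0.15 / √(0.75/16) = 0.693 SD.

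**3. The SAP rule.** For arm differences d1, d2, d3 at IPI, month 3 and month 6, with n = 30 per arm:

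lambda = (n/2) × Σ(dt − mean d)² / (1 − rho), on (2, 116) df.

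- *Constant benefit.* Every deviation is zero, so lambda = 0 and the rejection rate is 5% for any d, SD, rho or n. Simulation (5,000 runs each) gave 5.2%, 5.0% and 5.5% at rho 0.3, 0.5 and 0.7 for 0.693 SD, and 5.0%, 4.9% and 5.3% for 1 SD. A random-intercept mixed model with baseline as covariate gave 5.3% (150 runs).
- *Linear fade, 0.693 / 0.346 / 0.* Σ = 2 × 0.346² = 0.24, so lambda = 15 × 0.24 / (1 − rho) = 5.14, 7.2, 12.0.
- *Benefit gone by month 3, 0.693 / 0 / 0.* Σ = (2/3) × 0.48 = 0.32, so lambda = 15 × 0.32 / (1 − rho) = 6.86, 9.6, 16.0. No difference until month 6, then 0.693 SD worse in the intervention arm, gives the same values.

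**4. The month-6 contrast from the same baseline-adjusted model.** Noncentrality = d × √[(n/2) / (1 − rho²)]. At d = 0.693 and rho = 0.5 this is 0.693 × √20 = 3.10.

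**Probability of declaring an effect (rho 0.3 / 0.5 / 0.7)**

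| True arm difference (IPI, month 3, month 6) | SAP rule, 2 df | Month-6 contrast |
|---|---|---|
| 0.5, 0.5, 0.5 | 5 / 5 / 5% | 51 / 59 / 76% |
| 0.693, 0.693, 0.693 | 5 / 5 / 5% | 79 / 86 / 96% |
| 0.5, 0.25, 0 | 28 / 38 / 59% | 5% |
| 0.693, 0.346, 0 | 50 / 66 / 87% | 5% |
| 1, 0.5, 0 | 83 / 94 / 99.6% | 5% |
| 0.693, 0, 0 | 63 / 79 / 95% | 5% |

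The mixed model gave 61% for the linear fade from 0.693 SD at rho 0.5, against 66% from the formula.

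**The case against.** **Baseline may have been meant as an outcome row.** The SAP does not name the three time levels. Section 4.3 counts the pre-intervention visit as a level of timing, and section 4.5 speaks of change from baseline. The two degrees of freedom could be a slip for three. The interaction would then include change from baseline, and a constant 0.693 SD benefit would be detected 63%, 79% or 96% of the time (rho 0.3, 0.5, 0.7). This is a fair point about intent, but it contradicts the written degrees of freedom and puts baseline on both sides of the equation. It also cures only half the problem: the 3-df test still fires 58%, 75% or 94% of the time for a benefit of 0.693 SD that fades linearly to zero by month 6.

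**A real benefit need not be flat.** IPI falls about one month after baseline and the scale looks back 30 days, so the effect could be partial at IPI and grow. The 5% figure is exact only for a constant benefit. Growth helps to a varying degree: rising linearly from half to the full 0.693 SD gives 16%, 20% or 31%, while a profile of 0.25, 0.74, 0.74 SD gives 48% at rho 0.5. Power then depends on how much the benefit changes between visits, not on its size at month 6.

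**The SAP does not say that a non-significant interaction means no effect.** That is correct, and a fading effect is literally an effect on change over time. But the plan names no other test for H3. It speaks of comparing arms without naming the contrast.

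**This is a secondary outcome in a pilot.** True, and the primary electronic-monitoring comparison uses a t-test and is unaffected. This limits the consequences but does not make the rule correct. Protocol section 4.7 also gives parameter estimation for a larger trial as a main purpose, and the between-arm estimate is what is missing here.

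**Conclusion.** The concern holds. As written, the H3 rule does not test the hypothesis in SAP section 2. That a constant benefit is flagged only at the alpha level follows from the equation and needs no assumed figure. The false signal for a vanished benefit does depend on assumptions: with 30 per arm and rho from 0.3 to 0.7, a linear fade to zero at month 6 triggers the rule 28% to 59% of the time from 0.5 SD, and 83% to 99.6% from 1 SD. Reading baseline as a fourth outcome row restores power for a sustained benefit but not the match to the hypothesis, so the text needs correcting on either reading. The finding is confined to Secondary Outcome 2.

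**What to change.** Keep the model with the three post-baseline visits as outcome rows and baseline adherence as covariate, and name those visits in the SAP so that the two degrees of freedom are explicit. Define the H3 test as the 1-df baseline-adjusted arm contrast at month 6 (B1 plus the month-6 element of B3, with IPI as reference), reported as a between-arm difference with a 95% confidence interval. Keep the 2-df interaction as a description of whether the effect changes over time, and delete the sentence that makes it the decision rule. Within-arm changes can stay as supporting summaries.

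The cost is a few lines of SAP text and one contrast statement, with no new data. The SAP describes the trial partly in the past tense and already reports this sample's scale reliability, so the change should be dated and justified, and the interaction result reported alongside the new contrast.
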